APPENDIX B: RADIATION TREATMENT

This protocol allows for the following treatment modality options:

- External beam radiotherapy (EBRT) only
- EBRT and high-dose rate (HDR) brachytherapy (BT) combined

RADIOTHERAPY PROTOCOL FOR EXTERNAL BEAM RADIOTHERAPY (EBRT)

FACILITY AND EQUIPMENT

- The treatment centre shall have equipment for and previous experience with Intensity Modulated Radiotherapy (IMRT) and/or Volumetric Modulated Arc Therapy (VMAT).
- The make and version of the particular treatment equipment shall be reported to the QA-centre.

PATIENT POSITIONING AND SIMULATION

- Pre-treatment preparation
 - \circ $\;$ The patient shall be immobilized with at least leg fixation.
 - Among patients treated with EBRT, the patient reference coordinate system shall be defined by using implanted fiducial markers in the prostate.
 - In patients with rectum diameter > 4 cm at the level of the prostate due to faeces or flatus, a new planning CT/MR should be considered after emptying the rectum.
 - The bladder filling protocol should be according to local guidelines with the aim to keep the bladder comfortably filled during the whole RT series with a volume as close as possible to the filling during the treatment planning CT/MR.
- Pre-treatment imaging
 - For structure delineation, CT and (preferably MR imaging) shall be performed with the patient in the treatment position in his fixation device on a flat tabletop.
 - \circ The CT (and MR scanning) shall be performed from L3 to the lower border of trochanter minor.
 - Slice-thickness shall be maximum 3 mm.
 - Treatment planning dose calculations shall be performed based on CT but can also be based on MRI if this technique is implemented and verified at the particular treatment centre. In case MRI based treatment planning and dose calculation is used, any pre-processing of the imaging data (e.g. conversion to appropriate radiation interaction data) shall be reported.
 - \circ $\;$ Image sets from the different modalities in treatment position shall be co-registered.
 - Reference imaging for IGRT shall be made with well-defined reference system based on the internal fiducials.

VOLUME SELECTION AND DEFINITION

- The recommendations made by ICRU shall be followed.
- The naming of target and organs-at-risk volumes shall follow the Santanam et al IJROBP 83(4): 1344-1349, 2012.
- Target volumes:
 - Clinical Target Volume(s):
 - Prostate (CTVT1) shall include the prostate and any potential extra-capsular tumor growth.

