Table 2B. Dose prescription priorities for fractionation for schedule B

Priority	Structure	Prescribed	Dose-volume
		Dose (Gy)	recommendations
1	CTVT1 (Prostate)	72.5	D _{min} ≥ 68 Gy (97%)
2	CTVT3 (tumor involved ves)	66.7	D _{min} ≥61 Gy (97%)
3	PTVT1	72.5	D _{95%} ≥67 Gy (96%)
4	Rectum		V _{64Gy} < 20 %
5	PTVT1	72.5	D _{98%} ≥ 66 Gy (95%)
6	PTVT2	66.7	D _{98%} ≥ 59 Gy (94%)
7	CTVT2 (prox ves, 2cm)	52.2	D _{min} ≥43Gy (95%)
8	CTVN (Nodes)	52.2	D _{min} ≥43Gy (95%)
9	Rectum		V _{69Gy} < 15 %
10	ΡΤVΤ3	52.2	D _{95%} ≥43Gy (95%)
11	PTVN	52.2	D _{98%} ≥42 Gy (93%)
12	FemoralHeads_L/R		D _{2%} ≤ 51Gy
13	BowelBag		V _{28Gy} < 300 cm ³
14	Rectum		V _{37.5Gy} < 150 cm ³
15	Body-PTV		V _{42Gy} < 100 cm ³
16	Bladder		V _{46Gy} < 35 cm ³

Priority	Structure	Dose (Gy)	Dose-volume recommendations
1	CTVT1 (Prostate)	78Gy	D _{98%} ≥ 76 Gy (97%)
2	CTVT3 (tumor involved ves)	70Gy	D _{98%} ≥ 68 Gy (97%)
3	PTVT1	78Gy	D _{95%} ≥ 75 Gy (96%)
4	Rectum		V _{70Gy} < 20 %
5	PTVT1	78Gy	D _{98%} ≥ 74 Gy (95%)
6	PTVT2	70Gy	D _{98%} ≥ 66 Gy (94%)
7	CTVT2 (prox ves, 2cm)	50Gy	D _{98%} ≥ 47.5Gy (95%)
8	CTVN (Nodes)	50Gy	D _{98%} ≥ 47.5 Gy (95%)
9	Rectum		V _{75Gy} < 15 %
10	ΡΤVΤ3	50Gy	D _{95%} ≥ 47.5 Gy (95%)
11	PTVN	50Gy	D _{98%} ≥ 46.5 Gy (93%)
12	FemoralHeads_L/R		D _{2%} ≤ 55Gy
13	BowelBag		$V_{30Gy} < 300 \text{ cm}^3$
			$V_{40Gy} < 150 \text{ cm}^3$
			$V_{45Gy} < 100 \text{ cm}^3$
			$V_{50Gv} < 35 \text{ cm}^3$
14	Rectum		V _{60Gy} < 35 %
15	Body-PTV		D _{2%} ≤ 83 Gy (107%)
16	Bladder		D _{mean} ≤ 62 Gy (80%)

Table 2C. Dose prescription priorities for fractionation for schedule C

HDR-BOOST

Patients are anesthetized and vital functions are monitored with the patient lying in dorsal lithotomy position. HDR-BT shall be performed by introducing a thread-formed iridium-192 source into hollow steel needles perforating the perineum and placed into the prostatic gland. The needles are inserted by transrectal ultrasound guidance. The treatment plan should encompass the prostatic gland (CTVT1) and 2 mm isotrope margin to the PTVT1.

Table 3

Risk organ	Brachy regime	Constraints	Fraction dose/fraction	EQD2 HDR (α/β = 3)	EQD2 HDR-External RT $(\alpha/\beta = 3)$
Urethra	10 Gy x 2	Max. 11.5 Gy to 0.1 cc	11.5 Gy / 2	66.7 Gy	116.7 Gy
Urethra	15 Gy x 1	Max 16.8 Gy to 0.1 cc	16.8 Gy / 1	66.5 Gy	116.5 Gy
Urethra	10 Gy x 2	Max point dose 12 Gy	12 Gy / 2	72 Gy	122 Gy
Urethra	15 Gy x 1	Max point dose 17.5 Gy	17.5 Gy / 1	71.8 Gy	121.8 Gy

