Urethra	10 Gy x 2	Max 7.6 Gy to 2cc	7.6 Gy / 2	32.2 Gy	82.2 Gy
Rectum	15 Gy x 1	Max 11.3 Gy to 2cc*	11.3 Gy / 1	32.3 Gy	82.3 Gy
Rectum	10 Gy x 2	Max 6.6 Gy	6.6 Gy / 2	25.2 Gy	75.3 Gy

*Check visually =< 60% of rectal mucosa to 2cc

EQD2 for rectum and urethra (a/b=3Gy) is 50.8 Gy for 14.5 Gy x 1 and 54.0 Gy for 15.0 Gy x 1.

POST-OPERATIVE RADIOTHERAPY

ENDOCRINE THERAPY

150 mg of bicalutamide is administered for 18 months during and after post-operative radiotherapy, starting up to two weeks before the start of radiation treatment but after profylactic breast irradiation. PATIENT POSITION AND FIXATION

The patient will be treated in supine position. The position must be the same during planning, simulation and treatment.

The patient should be immobilized according to the standard procedures of each participating centre. The type of fixation device/technique shall be reported in the RTQA-report

PATIENT DATA ACQUISITION

A CT based simulation shall be made in the treatment position for all cases, on a flat table top and with the patient in his fixation device. CT scanning shall be performed with a slice thickness of maximum 3 mm. As an option, MR images that are co-registered with the planning CT images may also be used.

In patients with extremely filled rectum (> 4 cm) due to faeces or gas, new planning CT/MR should be performed prior to treatment planning. The bladder should be comfortably filled. Images will be obtained from at least the lower end of the sacroiliacal joints to 10 mm below the tuberositas ischii.

Delineation of target volumes and organs at risk (OAR) must be done on CT images, or together with MR images appropriately co-registered with planning CT images. RT will be delivered with megavoltage equipment at energies >= 6 MV, with daily fractions of 2 Gy/5 days per week.

TARGET VOLUMES AND ORGANS-AT-RISK (OAR) VOLUMES

The definition of volumes follows the recommendations made by ICRU in Report 50 and in the supplementary ICRU Report 62 and in ICRU Report 83 for photon beam therapy.

TARGET

Clinical target volume prostate bed CTVT

The CTVT will include the prostate bed in all patients.

Information which may be used to define the prostate bed CTV includes: Histopathologic information of prostate size and tumor extent to specific boundaries of the surgical resection, pre-operative imaging e.g. pelvic CT/MRI studies and post-operative anatomy on planning CT scan.

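### Table 3 (HDR boost): the 10 Gy x 2 limit of 7.6 Gy to 2 cc is labelled Urethra but is, on the table's own numbers, the rectal limit

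*Protocol*

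**What the plan says.** Appendix B permits two forms of primary radiotherapy, one of them "EBRT and high-dose rate (HDR) brachytherapy (BT) combined". Table 3, under the HDR-boost heading, gives the organ limits for that boost. Each row names an organ, a regime, a limit, the dose and number of fractions, the EQD2 of the HDR part, and the EQD2 with external radiotherapy added.

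Rows 1 to 4 are urethral and form two pairs, each listing 10 Gy x 2 first and 15 Gy x 1 second:

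- **0.1 cc:** 11.5 Gy x 2 (66.7 Gy), then "Max 16.8 Gy to 0.1 cc" (66.5 Gy).
- **Point dose:** 12 Gy x 2 (72 Gy), then "Max point dose 17.5 Gy" (71.8 Gy).

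Row 5 is labelled Urethra, 10 Gy x 2, "Max 7.6 Gy to 2cc" (32.2 Gy; 82.2 Gy with external). Row 6 is labelled Rectum, 15 Gy x 1, "Max 11.3 Gy to 2cc" (32.3 Gy; 82.3 Gy with external), with an asterisk leading to the note "Check visually =< 60% of rectal mucosa to 2cc". Row 7 is labelled Rectum, 10 Gy x 2, with a maximum of 6.6 Gy and no volume or point (25.2 Gy; 75.3 Gy with external).

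**The concern.** Rows 5 and 6 follow the pattern of the two urethral pairs (same volume, same order of regimes, near-identical EQD2), yet they carry different organ labels. If row 5 belongs to the rectum, the printed table does two things it was not meant to do. It leaves the 10 Gy x 2 regime without a rectal 2 cc limit. It also gives the urethra a 2 cc limit that has no counterpart under 15 Gy x 1.

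A centre planning 10 Gy x 2 from the printed labels would apply the 7.6 Gy limit to the wrong organ. Its only remaining rectal limit would be the 6.6 Gy row, which does not say where the dose is measured. Radiotherapy quality assurance would be checking compliance against the same mislabelled row.

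**Working it through.** **Inputs.** All doses, fraction numbers and EQD2 values are from Table 3. The alpha/beta of 3 Gy is in the column heads and in the note below the table: "EQD2 for rectum and urethra (a/b=3Gy) is 50.8 Gy for 14.5 Gy x 1 and 54.0 Gy for 15.0 Gy x 1".

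**Formula.** EQD2 = n x d x (d + 3) / 5, for n fractions of d Gy.

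**Reproducing the plan's figures.** The note: 14.5 x 17.5 / 5 = 50.75 and 15 x 18 / 5 = 54.0, as printed after rounding. The rows:

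| Row | Printed label | Limit (d x n) | Computed EQD2 (Gy) | Printed EQD2 (Gy) | d / fraction dose |
|---|---|---|---|---|---|
| 1 | Urethra, 0.1 cc | 11.5 x 2 | 66.70 | 66.7 | 115% |
| 2 | Urethra, 0.1 cc | 16.8 x 1 | 66.53 | 66.5 | 112% |
| 3 | Urethra, point | 12 x 2 | 72.00 | 72 | 120% |
| 4 | Urethra, point | 17.5 x 1 | 71.75 | 71.8 | 116.7% |
| 5 | Urethra, 2 cc | 7.6 x 2 | 32.22 | 32.2 | 76% |
| 6 | Rectum, 2 cc | 11.3 x 1 | 32.32 | 32.3 | 75.3% |
| 7 | Rectum, none given | 6.6 x 2 | 25.34 | 25.2 | 66% |

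The dose cells are sound. The one discrepancy is row 7, where 25.3 would also fit the printed total of 75.3 Gy (25.3 + 50); that is a separate small slip.

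**Pairing by iso-effect.** The two-fraction dose with the same EQD2 (E) as a single-fraction limit is d = (-3 + sqrt(9 + 10E)) / 2.

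- 16.8 x 1: E = 66.53, d = 11.48 (printed 11.5).
- 17.5 x 1: E = 71.75, d = 11.98 (printed 12).
- 11.3 x 1: E = 32.32, d = 7.61 (printed 7.6).

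In all three cases the 15 Gy x 1 limit returns the printed 10 Gy x 2 limit to 0.1 Gy. The EQD2 gaps within pairs are 0.17, 0.25 and 0.09 Gy, so rows 5 and 6 are the closest match of the three.

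**Looking for another partner.** Row 7 is the only other rectal row for 10 Gy x 2. Its single-fraction equivalent solves d(d + 3)/5 = 25.34, giving d = 9.86 Gy, so it does not pair with 11.3 Gy. No urethral 2 cc row exists for 15 Gy x 1, so row 5 as labelled has no partner.

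**Volume and dose level.** The 2 cc volume occurs only in rows 5 and 6, and the footnote ties it to the rectum ("of rectal mucosa to 2cc"). The undisputed urethral limits use 0.1 cc or a point and lie at 112% to 120% of the fraction dose. Row 5 lies at 76%, next to the rectal rows at 75.3% and 66%.

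**The case against.** The strongest counter-argument is that the text was read from a PDF. The doubtful label sits at the change from urethra to rectum, and a vertically merged organ cell in the original could have put it on the wrong row. Alignment also looks doubtful nearby: in Table 2B, the rows for rectum, body and bladder carry cut-offs in cubic centimetres that match the bowel entries of Tables 2A and 2C. The internal agreement of row 5's dose cells says nothing about its organ cell.

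This possibility stands and is why the original page must be checked first. It is not shown, however. Four urethral and three rectal labels that had merely shifted would not come out as five and two, and in Tables 2A and 2C the text leaves continuation cells blank rather than filling them.

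Two further points are fair. Pairing is not universal, because row 7 has no partner, and the asterisk is on row 6 only. Neither supplies another partner for 11.3 Gy x 1. Relabelling alone also leaves two rectal limits for 10 Gy x 2, one without a volume, so the 6.6 Gy row needs clarifying as well.

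On consequence, the objection is largely right. Read as a maximum, 6.6 Gy is stricter for the rectum than 7.6 Gy to 2 cc, so the printed table does not imply more rectal toxicity. The protocol gives no urethral volume from which to judge whether a 2 cc limit there would ever bind.

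**Conclusion.** The concern holds, as a minor internal inconsistency. Row 5 of Table 3 is the 10 Gy x 2 partner of the rectal 2 cc limit in row 6 and should be labelled Rectum. With that label the two regimes' rectal 2 cc limits agree at 82.2 and 82.3 Gy combined EQD2, and at 76% and 75.3% of the fraction dose.

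The protocol nowhere states the correct label, so this is an inference. It rests on the table's own alpha/beta of 3 Gy, the shared volume, the footnote and the dose level, which all point the same way. It assumes that the extracted text reproduces the printed organ column.

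The effect is confined to patients given the HDR boost as 10 Gy x 2. The primary endpoint, the sample size and the analysis are untouched.

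**What to change.** Check the original table. If the label stands as read here, change the organ in the 7.6 Gy row from Urethra to Rectum; no number changes. In the same correction, state the volume or point to which the rectal 6.6 Gy maximum applies, so that the two rectal limits for 10 Gy x 2 can be told apart, and notify the HDR centres. The cost is one row label, one short clarification and a notice.

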APPENDIX C: MAGNETIC RESONANCE IMAGING OF THE PROSTATE

For local staging of prostate cancer with MRI, the examination is performed at 1.5 or 3T using an external phased-array coil is sufficient. Imaging sequences consist of high-resolution T2-weighted images of the pelvis in three planes, diffusion-weighted sequences including an ADC-map and a dynamic contrast enhanced sequence during injection of a Gadolinium chelate contrast agent. This examination is sometimes referred to as "multiparametric prostate MRI". MR spectroscopic imaging is sometimes also included in this examination but not part of the minimal clinical standard.

The "Prostate Imaging – Reporting and Data System (PI-RADS) v2 document includes minimal requirements both for hardware, examination protocol and evaluation of MRI-images. For details, please see:

http://www.acr.org/~/media/ACR/Documents/PDF/QualitySafety/Resources/PIRADS/PIRADS%20V2.pdf)

The PI-RADS scoring system facilitates communication of findings on prostate MRI, both for localization of tumors within the prostate as well as grading of suspicion of malignancy. An example of PI-RADS scoring template is enclosed at the end of this section. If dynamic contrast is omitted the guidelines gives alternative PI-RADS scoring.

It is recommended that the MR-examination are evaluated by radiologists specialized in abdominal/prostate radiology and by those having continuous communication with physicians treating these patients.

Postoperative MDT conferences that discuss radiological, surgical and histopathological findings are advantageous in this setting.

	Pulse sequence	Orientation	Voxel size 1,5T	Voxel size 3T	Comment
1	Localiser				Buscopan 20mg iv. alt Glucagon 1ml im.
2	T2w_TSE_2D	Axial	4 x 0,5 x 0,5 alt 4 x 0,7 x 0,7	3 x 0,5 x 0,5	
3	T2w_TSE_2D	Coronal	4 x 0,5 x 0,5 alt 4 x 0,7 x 0,7	3 x 0,5 x 0,5	
4	T2w_TSE_2D	Sagital	4 x 0,5 x 0,5 alt 4 x 0,7 x 0,7	3 x 0,5 x 0,5	
5	T2w_TSE_3D	Coronal		0,7 x 0,6 x 0,7	Optional
6	EPI_DWI_2D	Axial	5 x 1,5 x 1,5 alt 4 x 2,0 x 2,0	4 x 1,0 x 1,0 alt 4 x 1,5 x 1,5	Adapted to quality of SNR: 50- 100 and 800–1000 s/mm2. For calculation of ADC, the highest b-value that should be used is 1000 s/mm2.
	Localiser				
10	T1w_calibration	Axial	1,5T 4 x 1,0 x 1,0 3T 4 x 0,7 x 0,7		Variable Flip Angle (VFA)
11	T1w_Spoiled gradient echo_3D	Axial	1,5T 4 x 1,0 x 1,0 3T 4 x 0,7 x 0,7		Dynamic 3 ml/sek Temporal resolution max 15 s

MR-imaging protocol (1.5T or 3T)

PI-RADS

- PIRADS 1 Very low (clinically significant cancer is highly unlikely to be present)
- PIRADS 2 Low (clinically significant cancer is unlikely to be present)
- PIRADS 3 Intermediate (the presence of clinically significant cancer is equivocal)
- PIRADS 4 High (clinically significant cancer is likely to be present)
- PIRADS 5 Very high (clinically significant cancer is highly likely to be present)

MRI-Reporting template SPCG-15 Name: Date:

PIN:

Prostate volum	າe:	_ml		
	Tumor 1	Tumor 2	Tumor 3	Tumor 4
Zone				
Lar gest diam mm				
EPE 1-5				
SVI (R/L) y/n mm				
Lower sphincter inv y/n				
Bladder neck invasion y/n				
PI-RADST2w(1-5)				
PI-RADSDWI(1-5)				
DCE-MRI (+/-)				
PI-RADS SCORE(1-5)				
Lymph nodes (mm)	R		L	
Bone metastasis y/n				

Reporting template SPCG-15 – Guide

- 1. Volume; HxLxW x 0.52
- 2. Largest diam mm; if in the peripheral zone measurement preferably tumor abutment of the capsule
- EPE; (ExtraProstatic Extension) 1-5. 1=EPE highly unlikely present, 2=EPE unlikely present, 3=EPE equivocal, 4=EPE is likely present, 5=EPE is highly likely present. EPE=4 and 5 can be included in SPCG-15, where (4) has a tumor/capsule interface (abutment) exceeding ≥12 mm together with a bulging capsule, irregular/spiculated capsule and (5) has signs of breach of the capsule with evidence of direct tumor extension.
- 4. SVI; (Seminal Vesicle Invasion) yes/no with mm growth above the upper part of the prostatic surface.
- 5. Lower sphincter invasion; Signs of or risk of apical tumor to invade the lower sphincter below the apex.
- 6. Bladder neck invasion; Signs of or risk of tumors at the base invading the bladder neck.
- 7. PI-RADS scoring according to the PI-RADS v2 found as pdf. at the reference listed above.
- 8. Template; v=ventral, d=dorsal, A=Base, B=Mid, C=Apex
